6.4 Reimbursement of subjects

In order to make participation worth the subjects' time, they will be reimbursed \$20 for the assessment sessions and \$50 for each MRI/TMS (total \$220/subject). We have found that this amount provides a good incentive to encourage ongoing participation.

6.5 Participant discontinuation/withdraw

During the pre-screening process, subjects who are found to be non-eligible, before signing the consent form, will be considered *not enrolled*, and all data related to that subject will be destroyed. Subjects who consent, and are found not eligible during the assessment and screening will be considered *screen failures*, and all research and identifying data will be destroyed, except for the consent form and limited information to document the screen failure (age, gender, diagnosis, specific reason for exclusion). Subjects will receive a subject number at the time of consenting. Subjects who pass screening will be considered *enrolled*. Subjects who leave the study after signing the informed consent, and after being deemed eligible/enrolled/randomized, will be considered *withdrawn*. Subjects may withdraw from the study at any time and for any reason. Subjects may be withdrawn by the investigator when continued participation would present an unacceptable risk to the subject. Based on previous experience, we expect that most subjects will be compliant with the study protocol.

7.0 Assessment of Safety and Regulatory Reporting

7.1 Data and Safety Monitoring Plan

7.1.1 Overall framework of monitoring: Study monitoring is conducted to ensure that the rights and well-being of trial participants are protected, that the reported trial data are accurate, complete, and verifiable, and that the conduct of the trial is in compliance with the currently approved protocol/amendment(s), with International Conference on Harmonization Good Clinical Practice (ICH GCP), and with applicable regulatory requirement(s)

7.1.2 Roles and responsibilities for regular operations

PD/PI: The PI, a board-certified psychiatrist, will meet with study staff on a weekly basis to monitor the progress of the study. During phases when subject recruitment is occurring, the PI will review screenings and scheduling of assessments, as well as strategies to improve recruitment yield. Issues around maintaining confidentiality and privacy of participants during screening, assessment and data collection will be reviewed. Any protocol deviations and adverse events will be reviewed at this weekly meeting. For serious adverse events, the PI will be notified as soon as the SAE comes to the attention of study staff.

Study coordinator/research assistant: This bachelors level individual will carry out the screening and informed consent, and they will provide additional study information, all under the supervision of the PI. The individual will be trained in screening, administering consent and information to the participants. Questions about eligibility will be discussed with the PI. This individual will administer surveys and neuropsychological tests, monitor the participants during the procedure and administer the experimental intervention (TMS). They will receive training in the administration of TMS to ensure they can safely operate the device, are aware of potential side effects and can execute the seizure protocol if this is necessary. They will conduct any necessary follow-up interviews.

Clinical Assessor: Screenings will include thorough assessment of psychiatric health by a masters-level clinician with experience in administration of psychiatric interviews. They will ensure the absence of any neuropsychiatric conditions in the subjects, as well as health conditions that would be a contra-indication to TMS or MRI procedures.

7.1.3 Frequency and type of other study monitoring:

Institutional Review Board monitoring: Approval of all procedures, advertisements and materials given to subjects will be secured from the University of Michigan IRBMED. Annual reviews will be conducted by IRBMED, including the number of subjects screened, enrolled and withdrawn. The IRB will also review protocol deviations, adverse events (according to the reporting timetable of IRBMED) and complaints that arise in connection with the study.

TMS Safety Committee monitoring: The TMS Safety Committee (see eResearch application for composition of group and charter) will review the protocol prior to initiation of the first subject. The committee will receive an initial report after the first 3 subjects, and then semi-annual reports afterwards. The reports will include a log of all adverse events recorded during the study, number of subjects studied, and details of the specific TMS protocols employed. The committee will also review protocol deviations and any unanticipated events reported to the IRB. If the committee has concerns about subject safety, these concerns will be conveyed to IRBMED.

Data monitoring: Data entry will be audited by study staff, who were not involved in primary data entry.

7.1.4 Adverse events arising in the course of participation:

7.1.4.1 Adverse Events Review: Monitoring will occur by the clinical study coordinator. The coordinator will then bring all possible AEs to the attention of the PI for evaluation, gradation and appropriate reporting. AE's will be assessed for severity (mild, moderate, severe), expectedness (expected, unexpected) and relatedness (definitely related, possibly related, unlikely related, not related). A log of all AE's will be maintained by the study coordinator.

7.1.4.2 Adverse Events Definitions and reporting timetable: A Serious Adverse Event (SAE) in this study will be defined as an event that results in death, is life-threatening, requires hospitalization or prolongation of existing hospitalization, or results in persistent or significant disability or incapacity. The degree of probable relation between study procedures and the SAE will be carefully evaluated and documented.

Serious adverse events will be reported to the IRB within 7 days of occurrence (or notification) of the event if they are definitely or possibly related to the study interventions and unexpected. If the SAE is expected, it will be reported within 14 days. For SAEs that are not related to the study, reporting will occur at the time of scheduled continuation, or not at all if determined to be expected, per standard reporting timetable of the University of Michigan IRB.

Unexpected adverse events in this study will be defined as any adverse events for which the nature and severity are not consistent with expected or anticipated adverse events resulting from participation in the protocol.

Adverse events will be assessed as severe, moderate or mild. Moderate is defined as any non-serious event which causes discomfort and requires treatment, but does not pose any significant or permanent risk or harm to the subject or require in-patient hospitalization, including social or psychological trauma causing moderate or temporary distress, significant embarrassment, stigmatization of individual or community/ group, disruption of familial/social relationships or nontrivial emotional distress or upset. Moderate AEs will include evaluation in the emergency room not leading to hospitalization. Mild is defined as any non-serious event of less than moderate severity.

Moderate and mild AEs that are expected will not be reported to the IRB. Moderate/mild AEs that are unexpected and definitely or possibly related will be reported to the IRB at the time

of scheduled continuing review. Moderate AEs that are unexpected and definitely not related will not be reported to the IRB.

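### The adverse-event rules allow a stimulation-induced seizure to be classed either as an SAE or as moderate, and the two classes carry very different reporting duties

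*Combined protocol and SAP*

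**What the plan says.** Section 7.1.4.2 defines an SAE as "an event that results in death, is life-threatening, requires hospitalization or prolongation of existing hospitalization, or results in persistent or significant disability or incapacity". An SAE that is related and unexpected goes to the IRB within 7 days, and an expected one within 14.

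The same section then sets the grades: "Adverse events will be assessed as severe, moderate or mild". Moderate is confined to non-serious events and to an event that "does not pose any significant or permanent risk or harm to the subject or require in-patient hospitalization". It adds a specific example: "Moderate AEs will include evaluation in the emergency room not leading to hospitalization". Severe is not defined and has no reporting deadline.

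On reporting below SAE: "Moderate and mild AEs that are expected will not be reported to the IRB". For the rest, "Moderate/mild AEs that are unexpected and definitely or possibly related will be reported to the IRB at the time" of the scheduled continuing review. Section 7.1.3 makes that yearly: "Annual reviews will be conducted by IRBMED".

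For the TMS Safety Committee, 7.1.3 says: "The committee will receive an initial report after the first 3 subjects, and then semi-annual reports afterwards". Those reports carry a log of all adverse events. The committee also reviews protocol deviations and unanticipated events that went to the IRB.

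Sections 9.3.1.3 and 9.3.2.3 both tag seizure induction as rare and serious, and 9.3.1.3 calls it the main safety concern with TMS. The seizure protocol in 9.3.2.3 ends with transfer to an emergency department and written documentation. It does not mention notice to the IRB or the committee.

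**The concern.** Seizure is the hazard that this study most needs to handle without ambiguity. The subjects are healthy volunteers with no direct benefit (9.4). The risk section calls the event serious, but the operative definition in 7.1.4.2 is a closed list of four outcomes that does not refer to that label. A provoked seizure that resolves, is assessed in the emergency department and is sent home need not meet any of the four, and its disposition matches the stated example of a moderate event.

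What is at stake is independent oversight, not the study team's awareness. The PI hears of any SAE as soon as staff do, and of every other event at the weekly meeting (7.1.2). Whether the IRB and the committee hear promptly depends on a grading choice that the text leaves open.

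**Working it through.** The plan states no figure to reproduce. The check is a trace of the event through the rules, followed by simple arithmetic for scale.

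**Trace: seizure during iTBS, emergency-department assessment, discharge**

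| Class given | IRB hears (7.1.4.2) | Committee hears (7.1.3) |
|---|---|---|
| SAE, related, unexpected | within 7 days | reviewed as an unanticipated event; no deadline stated |
| SAE, expected | within 14 days | next periodic report |
| Severe, not SAE | no rule | next periodic report |
| Moderate, related, unexpected | scheduled continuing review | next periodic report, or after the IRB report |
| Moderate, expected | not reported | next periodic report |

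*For the SAE rows:* section 9.3 calls seizure serious, moderate is limited to non-serious events without significant risk, and a PI could judge a seizure life-threatening.

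*For the moderate rows:* no listed SAE outcome need occur, and the emergency-room example fits the planned pathway.

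*For the severe row:* if the limits on moderate exclude a seizure and no SAE outcome is met, severe is the only grade left.

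The protocol does not say whether seizure is expected. It is a listed risk, but stimulation is capped at 80% of active motor threshold, well below the setting of the one TBS seizure cited in 9.3.2.3, which could make it unexpected.

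**Delay, in iTBS exposures**

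Assumptions: even accrual over 2 years (104 weeks) and up to 4 exposures per subject (the Visit 2 trial run plus Visits 3 to 5).

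- Total: 40 × 4 = 160; 60 × 4 = 240; 40 completers plus 20 with the trial run only, 160 + 20 = 180.
- Per week: 160/104 = 1.54; 240/104 = 2.31; 180/104 = 1.73.
- 7 days: 1.5 to 2.3. 14 days: 3.1 to 4.6.
- Semi-annual report: average wait 13 weeks, 20 to 30; longest 26 weeks, 40 to 60.
- Annual review: average wait 26 weeks, 40 to 60; longest 52 weeks, 80 to 120.

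These counts measure how long a body outside the study team may wait. They are not exposures given without supervision.

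**Chance of any seizure in the study**

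- At 1/30,000 per treatment (9.3.1.3, quoted there for depression therapy and applied here to each exposure): 1 − (1 − 1/30,000)^160 = 0.0053; with 240 exposures, 0.0080.
- At 1 per 1,000 TBS participants (9.3.2.3 gives one in over 1,000): 1 − 0.999^40 = 0.039; 1 − 0.999^60 = 0.058. This is likely too high here, because the cited seizure occurred at 100% of resting motor threshold.

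The documents give nothing from which to estimate how often a seizure would be graded below SAE, so no probability is attached to the slow route.

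**The case against.** The strongest reply is that the document, read as a whole, already treats seizure as an SAE. Section 9.3 labels seizure serious while marking scalp pain, headache and syncope as not serious, so the label is deliberate. The emergency-room sentence illustrates a category limited to non-serious events and need not override that limit. Expectedness in 7.1.4.2 depends on nature and severity together, and the listing that makes a seizure expected is the same one that calls it serious. Calling it both expected and moderate is therefore strained.

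Much of this stands. The SAE reading is reasonable and may be what was meant. But the SAE definition does not refer to the label in 9.3, the emergency-room sentence is explicit, and severe is left without meaning or deadline. The text permits the SAE reading without requiring it.

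A reader might go further and infer that the IRB would never hear of an expected seizure, or that the committee would hear only through a semi-annual log. The documents do not support either. Section 7.1.3 refers to the IRBMED reporting timetable, 7.1.1 commits to GCP and applicable regulation, and 5.0 commits to the abbreviated IDE requirements. None of these is reproduced, and any of them may require a report. A seizure among the first 3 subjects would reach the committee in its initial report. Nor does the lack of a stated pause after a seizure show that sessions would simply continue: the PI may withdraw subjects for safety (6.5), and the charter, held with a separate application, may contain a rule.

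**Conclusion.** The point holds as an inconsistency in classification. Section 9.3 calls seizure serious; 7.1.4.2 does not make it an SAE and offers a moderate category that fits its planned disposition. On one reading the IRB hears within 7 or 14 days. On the other it hears at continuing review, or not at all under 7.1.4.2, and the committee may hear only in its next periodic report.

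The practical size is small. At the plan's per-treatment rate the chance of any seizure is about 0.5% to 0.8%; the TBS participant rate gives 3.9% to 5.8%, probably an overstatement. The chance of a grade below SAE is unknown, and the unseen IRBMED timetable and charter may close part of the gap. The exposure counts also assume even accrual. The case for change rests on the event being the study's main hazard and on the correction costing almost nothing. It is a cheap improvement and does not imply that subjects would be left unprotected.

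**What to change.** In 7.1.4.2:

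- Add: *Any seizure during or after a TMS session, including motor threshold testing and the Visit 2 trial run, is an SAE whatever its disposition or expectedness, and is reported to the IRB within 7 days.*
- Exempt seizure from the sentence that classes emergency-room evaluation without admission as moderate.
- State that severe means SAE.

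In 7.1.3, after checking the committee's charter, add that any seizure is sent to the TMS Safety Committee at the same time as the IRB report. Keep the periodic reports as they are. Leave any pause in stimulation after a seizure to the committee and its charter; a rule written into the protocol could conflict with one already there.

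The cost is a few sentences and, if a seizure occurs, one extra notice. Design, sample size and analysis are unaffected.

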7.1.5 Quality assurance and quality control for data acquisition

Clinical assessments: Assessors will be trained on assessment instruments and established according to laboratory standards and good inter-rater reliability

MRI data: The fMRI lab maintains weekly schedule of calibration runs to assure consistent operation. Processing pipelines and standard operating procedures are in place ensure that data is processed in a uniform manner. Quality control at each step will be carried out by study staff to verify, through multiple metrics, image quality. Databases will track processing steps, in addition to automatically generated log files.

7.1.6 Confidentiality and security of data

Confidentiality of data: Multiple steps are taken to ensure the confidentiality of sensitive information. Subjects are reminded that they do not have to answer questions that make them feel uncomfortable, which reinforces the voluntary nature of their participation. The confidentiality of all information gathered directly from subjects or obtained from the patient's medical records is assured by assigning records a coded research number and identifying all computer and paper files only by this code. A single tracking file will link the codes with subject identifiers, such as name and hospital number. In addition, consent forms and payment forms will be kept in a separate, locked room, apart from research data. All files will be kept in locked file drawers in locked rooms, to which only authorized research personnel have access. Electronic records will be kept on secure servers, and records with identifying information will be kept separate from records used to collect research data. Only staff members who have a need to know personal identifying information will have access to this information. All research staff are trained in research ethics and HIPAA regulations pertaining to protected health information. Screening forms for subjects who do not qualify for the study will be destroyed, except for anonymous information unlinkable to the subjects (such as age, gender and education). After the completion of data analysis, the record linking subjects to the research codes will be destroyed, thereby anonymizing the data.

7.2 Event Windows, Missed Assessments, Missed Sessions and Protocol Deviation Reporting

Any safety-related assessments (TASS, fMRI screening) which are missed will be reported to the IRB as a protocol deviation. For the other assessments, missing assessments will not be reported as protocol deviations unless they constitute > 10% of the total assessments. In order to accommodate inevitable scheduling conflicts, holidays, etc., study team members will be allowed to schedule Motor Threshold (MT) and/or fMRI procedures with discretion as needed.

These deviations are expected to be minor and will not be reported, although they will be recorded. These allowances should affect neither the scientific integrity nor the safety monitoring provisions of the protocol.

8.0 Statistical analysis

Analyses described below represent planned analyses for primary and secondary measures. However, actual implementation of these analyses may differ slightly from what is described below, although the primary and secondary outcome measures will be as described.

Specific Aim 1: Localize neural effects of dIPFC iTBS

Primary outcome measures:

Primary outcome #1, BOLD activation: 2-back minus 1-back BOLD activation, voxelwise in FPN

Analysis Plan: MRI data analysis and strict quality control will use validated and established routines implemented in our laboratory. For processing BOLD images, we will use well-tested routines from FSL 5.0.1 and SPM12 for slice timing and realignment algorithms and spatial normalization (MNI-152) procedures implemented in VBM8. First-level analysis will use the general framework of the modified General Linear Model,(82) implemented in SPM12 with temporal convolution. For the *n-back* data the first-level design matrix will include regressors for 2-back and 1-back, iTBS/MRI session and 12 realignment parameters (including temporal derivatives of 6 realignment parameters). Second-level, between-subject analysis will consist of two-sided, one-sample t-tests for primary effects. For statistical inference across the FPN, and the entire brain, we will use topological false discovery rate (FDR)(83) providing corrected probabilities at $p<0.017$ ($0.05/3$, accounting for testing of 3 primary MRI measures). Given *a priori* hypotheses about FPN, a mask of activation (2-back minus 1-back, $p<0.001_{\text{uncorr}}$) at the group level, using all 4 MRI runs to provide the most representative mask, will be used as small volume correction.

(H1.1): iTBS to dlPFC, compared to vertex stimulation, will increase fMRI activation in the FPN during the n-back.

To examine the effect of iTBS on FPN, we will directly contrast the MRI session following dlPFC stimulation with the session following vertex stimulation, with subjects in an unconstrained, resting state for both conditions. (2-back minus 1-back contrast, voxelwise analysis in SVC-corrected FPN mask). We are using two-sided tests, because unpredicted results have been described in the literature, where inhibitory cTBS has resulted in increased perfusion,(42) and increased connectivity,(44) and excitatory 5 Hz TMS to dlPFC demonstrated reduced BOLD activation.(84) For a secondary measure to test H1.1, we will examine whole brain activation, since change may occur outside this region of interest. For example, dlPFC stimulation has been observed to induce changes in a limbic anterior-cingulate network.(85)

Exploratory analysis: We will conduct exploratory analyses with a generalized psychophysical interaction (gPPI). To test for interaction between task and session, we will extract the time-course at the site of stimulation, deconvolve it with the canonical hemodynamic response function (HRF), and then generate an interaction regressor (task X time-course) which is tested (after-reconvolution with HRF) across the entire brain.(86) gPPI tests for changes in the slope of connectivity coefficients with task, so it reflects how task modulates connectivity. Testing for effects of iTBS will test for a modulation of this modulation. Statistical correction will use topological false discovery rate (FDR)(83), at $p <0.05$, corrected for whole brain search.

Primary outcome measure #2, BOLD connectivity: FPN connectivity to dlPFC iTBS stimulation target

Analysis Plan: Data processing of fMRI BOLD resting scans will begin with standard pre-processing steps. All scans will be slice-time corrected and realigned (FSL 5.0.9) to the 10th image acquired during a scanning session.(87) Subsequent processing will be performed with the Statistical Parametric Mapping SPM8 package (R4667; Wellcome Institute of Cognitive Neurology, London). Anatomic segmentation will be performed with the VBM8 toolbox in SPM8, using the high resolution SPGR T1 image, subsequently normalized to an MNI template using DARTEL. Normalizing warps to the MNI152 template are applied to the co-registered functional volumes, which are re-sliced and smoothed with an 8 mm isotropic Gaussian smoothing kernel. To assess and manage movement, we will calculate the frame-wise displacement (FD (88)) from the translation and rotation parameters from the realignment file, which is the sum (in millimeters) of the absolute values of frame displacement, i.e. successive 3D volumes, for all 6 parameters of rotation and translation. Rotational displacements are converted from degrees to millimeters moved on the surface of a 50 mm sphere. We use a 'scrubbing routine' to censor

any frame with FD > 0.5 mm from the regression analysis described below, yielding a scrub ratio for each subject. As it has been demonstrated that as many as 60% of frames can be removed and still yield analyzable results,(88, 89) we will use 60% deleted frames as a cutoff for analyzable subjects. Three-compartment segmentation of the high-resolution structural image from the VBM8 normalization will be applied to the functional time series to extract cerebral spinal volume (CSF) and white matter (WM) compartments, which will be subjected to a principal component analysis to identify the top 5 components in each,(90) which corresponds to heart rate and respiratory effects on the blood oxygenation level-dependent signal.(91) Adjusted time courses will be derived from sequential regressions of the time series with the following: Linear trend, 6 motion parameters, their temporal derivatives, the quadratics of these 12 parameters, 5 components from the PCA of CSF, 5 components of PCA of WM, followed by band pass filtering from 0.01 – 0.1 Hz, and then motion scrubbing. ICA-AROMA will be used to de-noise the data and remove additional, residual motion artifacts.(92) Global signal regression (GSR) will not be done because of concerns about non-uniform transformation of correlations introduced by GSR, problematic for group comparisons.(93) For the primary analysis, the time-course from a 6 mm radius sphere at the site of stimulation will be entered into the multiple regression and correlated with every other gray-matter voxel time-course in the brain for each subject. Correlation coefficients are Z-transformed and then entered into the second level, between-subject analyses as two-sided, paired t-tests to compare between sessions. Statistical inference will be controlled as above.

(H1.2) iTBS to dlPFC, compared to vertex stimulation, will increase FPN connectivity during resting state BOLD. Because TMS effects are observed away from the site of stimulation,(38-41) we are testing functionally-defined FPN networks. We recognize that the FPN defined by n-back will not be identical to the FPN defined by a dlPFC seed-based connectivity, although the two significantly overlap.

Exploratory analysis, global brain connectivity: We will examine a graph-theoretic measure known as global brain connectivity (GBC).(94) GBC reflects the strength of local connectivity, similar to degree connectivity, except that no arbitrary thresholding of connections ('edges') is required; rather, the value of the connection strength (r-to-Z transformed) is summed. GBC in the dlPFC has been shown to decrease with electro-convulsive therapy, with the degree of change related to symptom improvement;(95) thus, we will test to see if iTBS to the dlPFC has an effect on GBC in the dlPFC. Two types of analyses will be conducted. In the first, we will average the connectivity for the 6 mm radius sphere at the site of stimulation and compare that for dlPFC stimulation and vertex stimulation. Alpha level will be $p < 0.05$, two-sided. In the second analysis, we will search for network effects. Time courses will be extracted from 10 mm diameter spheres based on a set of 264 nodes distributed throughout the brain,(96) generating a cross-correlation matrix of Pearson r-values. Z-transformed r-values (connectivity strengths) for each of the 264 nodes with every other node (global brain connectivity) are summed, and connectivity strengths with the nodes within 13 specified networks are also summed. Connectivity measures (13 per subject) will then be entered into second level repeated measures ANCOVA, with gender as between factor, network and session (dlPFC, vertex) as within-factors, and meanFD and age as co-variates, testing the hypothesis of change in GBC by network. We will also test exploratory effects across all 13 networks (with alpha level set to $0.05/13=0.0038$), and we will test for effects on GBC (connectivity between all nodes).

Primary outcome measure #3, rCBF at stimulation target

Analysis plan: The *pCASL* images will be realigned using SPM12 realignment routines and denoised using compCor(90) and then used to calculate the perfusion rate at each voxel using a

two-compartment model, assuming gray matter T1 of 1400 ms. and 90% labeling efficiency. ROI analysis of the CBF images will occur in native space, using the FPN mask derived from n-back activation, warped to individual anatomy. A two-sided, paired t-test will test for effect of sessions, with $p < 0.017$ as alpha. Secondary analyses will be performed on 6 cm radius sphere at the site of stimulation, in addition to a whole brain, voxel-wise search for changes in gray-matter tissue, using topological FDR to correct for multiple comparisons to $p < 0.017_{\text{corr}}$.

(H1.3) iTBS to dlPFC, compared to vertex stimulation, will increase resting perfusion at the site of stimulation. PET studies of high frequency TMS have reported increased CBF at the dlPFC,(97) a finding which motivates our hypothesis here. However, a cTBS study by our co-investigator ([name]) also found *increased* CBF after supposedly inhibitory stimulation of dlPFC,(98) so we will be performing a two-tailed t-test here. While the primary analysis will focus on the site of stimulation, a secondary analysis will focus on the FPN network, defined by the n-back task.

Exploratory analysis, amplitude of low frequency fluctuations (ALFF): ALFF, and fractional ALFF (fALFF), measures the magnitude of low frequency BOLD fluctuations, generally from 0.01 to 0.1 Hz.(99) fALFF measures the fractional strength (relative to the full spectrum) of BOLD fluctuations. ALFF is correlated with CBF,(100, 101) so this measure provides an alternative to supplement the pCASL analysis. This is a potentially important measure for brain stimulation, as fALFF/ALFF abnormalities have been reported in psychiatric disorders,(102-104) and fALFF in the subgenual cingulate gyrus has been shown to predict response to electroconvulsive therapy.(105) This analysis will use the BOLD resting data as above, except that frame censoring (scrubbing) will not be performed, since censoring can affect the frequencies in a run of BOLD-acquired MRI data. Each voxel's BOLD time series will be transformed into the frequency domain and the mean amplitude of the spectrum over the frequency range of 0.01–0.1 Hz will determine ALFF. fALFF for two bands (slow-4; 0.027-0.073 Hz; and slow-5, 0.01-0.027 Hz) will be calculated as the magnitude for that band over the magnitude of the full spectrum. This analysis will focus on the 10 mm diameter sphere under the site of stimulation. Alpha level for this analysis will be set at 0.017 (0.05/3), two-tailed.

Exploratory analyses, between measures: Exploratory analyses will also test for correlations between the three MRI measures, to provide a richer picture of iTBS effects. Lastly, we recognize that vertex stimulation, here being used as a control condition for dlPFC stimulation, may have some effects on brain networks, although it was selected to avoid the FPN. With some caveats (effect of order, since baseline is not counter-balanced), we can use baseline measures from the first MRI session (no preceding TMS session), to see if iTBS differences represent a change in the dlPFC-stimulated condition or the vertex-stimulated condition. An additional exploratory analysis will compare stimulation over the 'activated target' (2-back minus 1-back) versus the 'deactivated target' (1-back minus 2-back), based on how the target was selected.

Specific Aim 2: Demonstrate modulation of the effect of dlPFC iTBS by a cognitive task

Primary outcome measures:

To examine state-dependency and modulation of iTBS effects by task, we will contrast MRI measures following iTBS applied to the dlPFC while subjects perform the n-back with MRI measures following iTBS compared to when they are in an unconstrained, resting state. The general analysis plan will use the same work-up of the imaging data as described above, the only difference being the MRI sessions that are compared with each other. Although directions of change are difficult to predict, we are predicting increasing activity as has been reported for iTBS applied during a deep encoding memory paradigm and not observed during shallow-encoding.(106) However, it is possible that cortex may become more efficient and less activation may be seen. The following primary hypotheses will be tested:

Primary outcome #1, BOLD activation: 2-back minus 1-back BOLD activation, voxelwise in FPN
(H2.1) For dlPFC stimulation during performance of a n-back task, compared to dlPFC
stimulation in a resting, unconstrained mental state, FPN activation to the n-back task will be
greater. For this analysis, the region of interest will be the FPN taken from the activation mask,
as described above. For a secondary measure to test H2.1, we will examine whole brain
activation, since change may occur outside this region of interest.

Primary outcome measure #2, BOLD connectivity: FPN connectivity to dlPFC iTBS stimulation
target

(H2.2) For dlPFC stimulation during performance of a n-back task, compared to dlPFC
stimulation in a resting, unconstrained mental state, connectivity with the dlPFC site of
stimulation will increase. For this analysis, the region of primary interest will be connectivity to
site of stimulation.

Primary outcome measure #3, rCBF at stimulation target

(H2.3) For dlPFC stimulation during performance of a n-back task, compared to dlPFC
stimulation in a resting, unconstrained mental state, resting perfusion at stimulation site will
increase. The primary region of interest will be the site of stimulation, and secondary analyses
will focus on the FPN, defined by n-back activation.

Specific Aim 3: Demonstrate improvement in cognitive control with iTBS, modulated by cognitive task during stimulation

Primary outcome measure: accuracy to 2-back

Analysis plan: For analysis of n-back performance, our primary performance measure will be accuracy to the 2-back condition. Secondary measures will be d-prime, to capture the sensitivity to the target and not bias to respond, and median reaction time. Although we found significant effects on d-prime for our list learning paradigm, that memory task was very different from the more demanding n-back, which requires updating and manipulation in short-term storage, while our list learning task involved only incidental memory. For each measure, we will conduct a repeated measures ANCOVA, with the performance measure across the three iTBS conditions as the repeated measure, and sex as a fixed, between-subject factor and age as a co-variate. Post-hoc, paired t-tests will be used for specific contrasts.

(H3.1) 2-back accuracy will be greater for dlPFC stimulation (no task during iTBS) relative to vertex stimulation

(H3.2) 2-back accuracy will be greater for dlPFC stimulation applied while subjects carry out an n-back during iTBS stimulation during stimulation, compared to when they receive stimulation alone. The same hypotheses will be applied to d-prime, our secondary measure. Two-sided tests will be used, because it is also possible that performance may worsen, either with stimulation alone, or when combined with subjects performing the n-back. It would be critical to know, for example, that performance of a cognitive control task was degraded by combining TMS with a task. Although a commercial device is being tested on dementia patients, relying on the assumption that the combination is beneficial,(18) we are not aware of this assumption being tested as we propose to do here.

Exploratory analyses around performance correlations: In addition to testing questions about performance, we will also examine correlations between performance and the MRI measures from Aims 1 and 2, testing important questions around mechanism. Since we will systematically test for correlations between both performance measures and the three primary measures from each aim (18 correlations), alpha will be set at $0.05/18 = 0.0028$.

